(i) Extrapyramidal side effects (EPSE) measured with the Simpson-Angus Scale (SAS). The modified SAS used in ATLAS measures nine extrapyramidal signs: gait, arm dropping, shoulder shaking, elbow rigidity, wrist rigidity, leg pendulousness, glabellar tap, tremor and salivation, all of which are assessed by direct examination. Each item is rated on a scale of 0-4, with higher scores indicating greater severity of EPSE. The scale range of the modified SAS is thus 0-36. The SAS has been widely used to measure EPSE within clinical trials and will be administered at baseline, then again at week 4, weeks 10-12, week 16 and weeks 22-24 (initially 34-36). The change in SAS between baseline and week 10-12 and between week 10-12 and the final assessment (week 22-24 or 34-36) will be compared between groups to assess EPSE.

(ii) **Compliance** expressed as treatment discontinuation rates and as percentage of prescribed trial medication taken between weeks 1 and 10-12 and between weeks 13 and the final assessment will be compared in patient allocated to receive amisulpride and those allocated placebo.

(iii) Quality of life measured with the self-rated, 26-item, WHO Quality of Life Scale (WHOQOL-BREF) at baseline, 10-12 weeks and the final assessment. The WHOQOL-BREF includes two items about an individual's overall perception of their quality of life and health and questions assessing four

domains; physical, psychological, social and environmental well-being, which higher scores denoting a better quality of life.

A separate analysis plan for the cost-effectiveness will be drafted.

Sample size considerations

Because of the likely problems with recruitment and retention of patients with late-onset, schizophrenia-like psychosis, ATLAS included an initial Feasibility Phase following which, a pragmatic decision was made to reduce the target sample size from 200-300 to at least 100 participants, to be recruited by mid-2016. The statistical power calculations have been amended with the main emphasis being to answer the primary stage 1 question of whether 12 weeks of amisulpride provides worthwhile benefit. The minimal clinically relevant difference (MRD), given the potential hazards of antipsychotic drugs, is considered to be 5 points on the BPRS. We estimate that the standard deviation of BPRS scores will be 9 points. We are thus powering the trial on a minimal worthwhile standardised effect size of 0.56 (=5/9) standard deviations, a moderate treatment effect.

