With 100 patients, allowing for a 10% drop-out rate by 12-weeks, i.e. 90 of 100 with outcome assessments, ATLAS would have 70% power at 2p<0.05 to detect the MRD of 5 points between those taking amisulpride and placebo in stage 1, and ample power to detect larger differences.

4. General considerations

Study population:

Primary analyses of each stage will include all patients who have taken any study treatment in that stage. Participants who withdrew after pack allocation but before receiving any treatment can be safely excluded as treatment allocation is double-blinded so treatment allocation cannot influence the decision to withdraw and so introduce selection bias. Analyses of this population will be by intention to treat (ITT), ie all participants will be analysed in the treatment arm to which they were randomised, whether or not they adhered to the treatment. This is to avoid any potential bias in the analysis. Secondary analysis such as 'per protocol' (only those participants who adhere with the treatment allocation) may be carried out but as a sensitivity analysis only.

P-values:

Unless otherwise specified, estimates of amisulpride efficacy will be presented with 95% confidence intervals. P-values will be from two-sided test. No corrections for multiple testing will be made in the primary analyses.

Missing data:

The primary endpoint will be analysed using repeated measures analyses of all available data, which minimises impact of missing data. If a score is missing for a participant it is just missing. It has no effect on the other scores from the same participant.

Late data:

The week 4 and week 16 assessments should, where possible, be undertaken within ± 7 days of the scheduled date. The other assessments (e.g. 10-12 week and 22-24 week) allow a ± 14 day leeway. As deviations from scheduled assessments are possible in a study of participants with very late-onset schizophrenia-like psychosis assessments outside these windows will be included as if at the specified time point with no specified time limit.

Timing of interim analyses:

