The main analysis will be undertaken once all patients have reached 22-24 weeks from randomisation. To assess the efficacy of 12 weeks of amisulpride in Stage 1, the primary outcome of BPRS will be compared using repeated measures regression model. Data from week 4 and week 12 will be the outcome variables and baseline scores will be entered into the model as a covariate. Time will be modelled as a categorical variable. The comparison will be between active amisulpride treatment (arms A and B group together) and placebo (arm C). The six minimisation factors (age, gender, home circumstance, BPRS score, time since onset of symptoms and previous antipsychotic treatment) will also be included as covariates in the repeated measures model. A time by treatment interaction parameter will be included to examine if there is any changing treatment effect over time. Treatment effects are presented with 95% confidence interval and associated p-values in each case. For these analyses a p-value of 0.05 (5% level) will be used to indicate statistical significance. This analysis uses all available visit data which will maximise statistical power to detect any difference at visits

To assess the value of continuing treatment in Stage 2, arm A (amisulpride – amisulpride) will be compared with arm B (amisulpride – placebo). Most patients will have only one outcome time point at week 24 or 36; the protocol has now been amended to shorten Stage 2 to 12 weeks with an additional assessment at about week 16. So, an analysis of covariance will be carried out, using the week 12 BPRS as baseline into the model as a covariate. Confidence intervals for the difference in means will be calculated. Participants who withdraw in Stage 1 will not be included in this analysis.

The BPRS covers the important symptoms elicited in very late-onset schizophrenia-like psychosis patients. In particular the Hostility, Suspiciousness, Hallucinations, Unusual Thought Content, Tension, and Uncooperativeness items of the BPRS all assess important areas of psychopathology in

these patients. The 7-point rating of the BPRS on each of these items generates a sub-score for these six symptoms domains that the protocol pre-specified as those most likely to be affected by the disorder. Scores on the subset range from 6 to 42, with higher scores indicating greater levels of psychopathology. The sub-score will be analysed in the same way the full BPRS analysis, for both Stage 1 and Stage 2.

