5.2 Secondary endpoints:

The Simpson-Angus Scale (SAS) is used to see if amisulpride is having an effect on Extrapyramidal side effects (EPSE). The change in SAS scores will be plotted over time to see if there appears to be any increases over time. If the SAS scores remain constant over the assessment time points we can assume that amisulpride is having no effect on Extrapyramidal side effects.

Other continuous measures (EQ-5D and WHOQOL-BREF) will be analysed using the same methods specified in section 5.1, analysis of covariance.

5.3 Sensitivity analyses:

For assessment of change at week 12, analyses will be undertaken carrying forward week 4 assessments for patients with week 4 but not week 12 assessments. To evaluate the effect of compliance on treatment efficacy, the primary analysis will be repeated on a sub-group of participants who adhere to their allocated treatment arm but such analyses are prone to bias so will be interpreted appropriately cautiously.

5.4 Planned subgroup analyses:

Subgroup analyses will be limited to the same variables pre-specified in the protocol as minimisation variable used to balance randomisation:

- Age (60-69, 70-79, 80+)
- Gender
- Home circumstance (Living with spouse/partner, living alone, other)
- BPRS score (30-39, 40-49, 50+)
- Time since onset of symptoms (<6 months, ≥6 months)
- Previous antipsychotic treatment (No, Yes >1 month previously, Yes ≤28 days ago)

These exploratory subgroup analyses will be undertaken, appropriately cautiously, to investigate any influence of the prognostic factors. These subgroups will use standard test for significance of the parameter as an interaction in the repeated measures model.

Any deviations from this plan will be described in the final report.

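### The Stage 2 co-primary model names only week 12 BPRS as a covariate, while Stage 1 also adjusts for the six minimisation factors; if those factors are prognostic, the Stage 2 interval is wider than it need be

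*SAP*

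**What the plan says.** The SAP (section 3, Outcome measures) makes two BPRS changes co-primary: baseline to week 10–12, and week 10–12 to the final assessment. Section 5.1 gives each its own model.

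- **Stage 1 (A+B v C).** Repeated measures on weeks 4 and 12, with baseline BPRS as a covariate. The six minimisation factors (age, gender, home circumstance, BPRS, time since onset, previous antipsychotic treatment) "will also be included as covariates in the repeated measures model".
- **Stage 2 (A v B).** "So, an analysis of covariance will be carried out, using the week 12 BPRS as baseline into the model as a covariate". No other covariate is named. Patients who withdraw in Stage 1 are left out.

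Section 5.4 confirms the role of these variables, calling each a "minimisation variable used to balance randomisation", and later refers to them as prognostic. The six-item BPRS sub-score follows the full-scale analysis in both stages. Section 5.2 adds: "Other continuous measures (EQ-5D and WHOQOL-BREF) will be analysed using the same methods specified in section 5.1, analysis of covariance".

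**The concern.** Minimisation makes A and B more alike on the six factors than chance would. A model without them leaves their variation in the residual, so the standard error allows for between-arm differences that the design has largely removed. To the extent that the factors are prognostic, the interval is then too wide and the test runs below its nominal 5%. Stage 2 uses two of the three arms, so any lost precision falls on the smaller of the two co-primary comparisons, for which the SAP states no power.

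The two co-primary models also differ without explanation. A reader cannot tell whether the difference is deliberate, and the covariate set could be settled after results are known.

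**Working it through.** **1. The plan's own figure.** Section 3 states: "The minimal clinically relevant difference (MRD), given the potential hazards of antipsychotic drugs, is considered to be 5 points on the BPRS" and "We estimate that the standard deviation of BPRS scores will be 9 points". With 90 of 100 patients assessed, "ATLAS would have 70% power at 2p<0.05 to detect the MRD of 5 points". The allocation ratio is not stated. With equal arms the Stage 1 comparison is 60 v 30:

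SE = 9 × √(1/60 + 1/30) = 2.01; 5/2.01 = 2.48; power = Φ(2.48 − 1.96) = 0.70.

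A 45:45 split gives SE = 9 × √(2/45) = 1.90 and power 0.75, so the stated 70% implies 2:1, that is, three equal arms. Stage 2 then has at most about 30 per arm.

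**2. Assumptions not in the SAP.** Week 12-to-final correlation 0.6; partial R² (the share of variance left after week 12 BPRS that the factors explain) from 0 to 0.3; biased coin 0.8 in the minimisation; 90% or 60% of arms A and B analysed (about 30 or 20 per arm).

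**3. Hand calculation, 30 per arm.** Residual SD after week 12 BPRS = 9 × √(1 − 0.6²) = 7.2. SE = 7.2 × √(2/30) = 1.86. With 57 residual df (t = 2.00), the 95% half-width is 3.72. If balance on the factors were perfect, the true SE would be 1.86 × √(1 − R²), and the test would in effect use a critical value of 2.00/√(1 − R²):

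- R² 0.2: 2.00/0.894 = 2.24, two-sided error about 2.5%.
- R² 0.3: 2.00/0.837 = 2.39, two-sided error about 1.7%.

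Real minimisation balances less than perfectly, so simulation is needed.

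**4. Simulation with all factors as categories.** Degrees of freedom are 2+1+2+2+1+2 = 10. N = 100, three-arm minimisation, 1,500 runs per cell, true difference 5 for power. Each pair is week 12 BPRS only v week 12 BPRS plus factors.

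| Per arm | Partial R² | Power | 95% half-width | Type I error, week 12 only |
|---|---|---|---|---|
| 30 | 0 | 75% v 73% | 3.74 v 3.86 | 5.9% |
| 30 | 0.1 | 76% v 77% | 3.75 v 3.67 | 4.9% |
| 30 | 0.2 | 76% v 82% | 3.74 v 3.42 | 2.3% |
| 30 | 0.3 | 76% v 86% | 3.75 v 3.22 | 2.6% |
| 20 | 0 | 53% v 46% | 4.71 v 5.19 | 5.1% |
| 20 | 0.1 | 56% v 53% | 4.69 v 4.91 | 4.5% |
| 20 | 0.2 | 55% v 56% | 4.69 v 4.63 | 4.8% |
| 20 | 0.3 | 57% v 63% | 4.70 v 4.35 | 4.1% |

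Monte Carlo SE is about 1.1 points on power (√(0.75 × 0.25/1500)) and 0.6 on type I error (√(0.05 × 0.95/1500)).

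**5. Simulation with age and baseline BPRS continuous.** Degrees of freedom are 1+1+2+1+1+2 = 8; 1,000 runs per cell. Power, week 12 only v adjusted:

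| Per arm | R² 0 | R² 0.1 | R² 0.2 | R² 0.3 |
|---|---|---|---|---|
| 30 | 74% v 71% | 77% v 77% | 74% v 81% | 76% v 85% |
| 20 | 57% v 49% | 55% v 53% | 58% v 60% | 56% v 64% |

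At 30 per arm the week-12-only type I error was 3.4% at R² 0.2 and 2.7% at 0.3. A further run of the same 8-df form gave half-widths of 3.76 unadjusted against 3.43 (R² 0.2) and 3.20 (R² 0.3) adjusted: 3.76/3.43 = 1.10 and 3.76/3.20 = 1.175.

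**6. Dependence on the assumptions.** In the formula in step 3 the correlation multiplies both widths equally, so the relative widening does not depend on it. The power levels do.

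**The case against.** A reader might infer that the Stage 2 interval is certainly too wide and power certainly lost. The SAP does not support that. It gives no figure for what the factors predict beyond week 12 BPRS, and one of them, baseline BPRS, may overlap with the week 12 score already in the model. If the factors add nothing, adjustment widens the interval.

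Retention matters too. The 10% loss in the sample size section is drop-out by week 12, and Stage 2 was shortened because of numbers still on treatment at the final assessment. At about 20 per arm, adjustment costs power when the factors are weak, and the one-covariate model may then be the better choice. Losing patients also weakens the balance on which the conservatism rests: in the 20-per-arm rows, type I error without the factors is 4.1–5.1%. The two effects should not be added together.

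Other objections stand in part. The SAP never says that week 12 BPRS is the sole covariate; that is read from its silence, though the factors are spelled out for Stage 1 just above. A reader might also infer that the omission carries over to EQ-5D and WHOQOL-BREF. Section 5.2 points to the methods of 5.1 generally, which could include the Stage 1 covariates, and also names analysis of covariance, a term 5.1 uses only for Stage 2. The text is ambiguous and establishes neither reading.

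Finally, the error described is conservative: it is no evidence of bias or of excess false positives. The SAP puts its main emphasis on Stage 1, which is adjusted.

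None of this explains why two co-primary outcomes from one minimised allocation have different covariate sets.

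**Conclusion.** The inconsistency is real and unexplained; the loss from it is conditional. At about 30 per arm, with the factors explaining an assumed 20–30% of the variance left after week 12 BPRS, omitting them gives a type I error of about 2–4%, an interval about 10–17% wider than the adjusted one, and about 5–10 points less power for a 5-point difference. At 0–10%, the two models are within about 3 points of power of each other in either direction. These sizes rest on the assumed partial R², correlation, biased coin and retention, none of which the SAP gives. Adjusting as in Stage 1 is a cheap improvement, not the repair of an invalid analysis.

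**What to change.** In section 5.1, state that the Stage 2 analysis is an ANCOVA of final BPRS, A v B, adjusted for week 12 BPRS and the six minimisation factors, with age and baseline BPRS as continuous terms and the other four factors as categories. In section 5.2, state that EQ-5D and WHOQOL-BREF use the same covariates plus the measure's own baseline. If the sponsor prefers to leave the factors out of Stage 2, the SAP should say so and give the reason before unblinding.

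The cost is SAP wording; Stage 1 already uses every variable. The statistical price is about 8 degrees of freedom rather than 10. If the factors are not prognostic, the interval is about 2–4% wider at 25–30 per arm. At about 20 per arm it is about 8% wider (about 11% with all 10 df), with up to about 8 points of power lost.

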ATLAS A pragmatic randomised double-blind trial of Antipsychotic Treatment of very LAte-onset Schizophrenia-like psychosis

ATLAS

Statistical Analysis Plan

Version Number: 1.0

Prepared by: [name] and [name]

1. Introduction

This document gives a detailed statistical analysis plan for the ATLAS trial, and should be read in conjunction with the current protocol.

2. Background

Very late-onset schizophrenia-like psychosis is a common condition, which affects an estimated 34,000 of the UK population aged over 60 and with 2,800 new service contacts each year. After dementia and depression, these patients represent the largest diagnostic group presenting to Old Age Psychiatry services. Impairments in quality of life associated with psychosis are severe and comparable to those seen in younger schizophrenia patients and elderly people with dementia. Patients often suffer the effects of their delusional beliefs for 10 or 20 years and this has a negative impact upon their families, neighbours and local social and housing services.

Antipsychotic drugs are widely used to treat late-onset (i.e. age ≥ 60) schizophrenia-like psychosis patients but this practice is not evidence-based. A Cochrane review concludes that there is no reliable clinical trial evidence upon which to base treatment guidelines. Potential benefits of antipsychotic drugs cannot currently be quantified without proper clinical trial evaluation and need to be balanced against potential risks of such treatment. A large randomised trial is urgently needed to assess reliably the balance of benefits and risks of antipsychotic drugs in late-onset schizophrenia-like psychosis.

3. Trial objectives and design

ATLAS is a multi-centre randomised controlled trial with the following objectives:

Primary objectives

- 1) To determine whether 12 weeks' treatment with amisulpride is superior to placebo in reducing symptoms of very late-onset schizophrenia-like psychosis as measured by the Brief Psychiatric Rating Score (BPRS) and by numbers of patients withdrawn to open treatment by their physicians because of perceived lack of efficacy. A prior hypothesis is that benefits of amisulpride will be most apparent on hostility, suspiciousness, hallucinations, tension, uncooperativeness and motor hyperactivity sub-scores of the BPRS.

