- 2) To determine whether any benefits of amisulpride are maintained by prolonging treatment beyond 12 weeks. Duration of stage 2 treatment was initially 24 weeks but was then reduced to 12 weeks, to enhance numbers still on treatment at their final assessment.

Secondary objectives

ATLAS will also investigate:

- (i) The associated risks of side-effects and serious adverse events;
- (ii) Compliance with allocated treatment;
- (iii) The effects of treatment on quality of life;
- (iv) The cost-effectiveness of amisulpride treatment.

Trial design

ATLAS is a pragmatic, randomised, 3-arm, double-blind placebo-controlled trial with two stages:

Stage 1 – an initial double-blind placebo-controlled stage to investigate efficacy and tolerability of oral amisulpride (arms A and B) versus placebo (arm C) over 12 weeks.

Stage 2 – a second double-blind stage investigating the effects of treatment continuation (arm A) versus switching to placebo (arm B) over a further 24 (initially, later 12) weeks.

Randomisation (3 Groups)

 Stage 1 – Weeks 1-12	 Stage 2 – Weeks 13-24 (or 36)	
(A) Amisulpride		Amisulpride
(B) Amisulpride		Placebo
(C) Placebo		Amisulpride

Outcome measures

Primary Efficacy Parameter – Brief Psychiatric Rating Scale

The first primary outcome measure is the Brief Psychiatric Rating Scale (BPRS), a widely used clinician-rated instrument for assessing positive, negative and affective symptoms in patients with psychotic disorders. The BPRS consists of 18 symptom constructs. Each item is assessed by the rater on a 7-point scale ranging from 1 (not present) to 7 (extremely severe). The total score is obtained by summing the scores from the 18 items. Scores thus range from 18 to 126, with higher scores indicating greater levels of psychopathy. The BPRS will be administered at baseline, at week 4, then again in weeks 10-12, week 16 and the final assessment (weeks 22-24 or 34-36). Change in BPRS score between baseline and the week 10-12 assessment and between the week 10-12 and final assessments are the trial's co-primary outcomes.

The second primary outcome measure is the proportion of patients withdrawn to open treatment by their physicians because of perceived lack of efficacy.

Secondary Efficacy Parameters

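### The plan hypothesises that benefit is greatest on six BPRS items but tests those items only against zero, so it has no formal test of that comparative claim

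*SAP*

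**What the plan says.** SAP section 3, primary objective 1, sets out the hypothesis: "A prior hypothesis is that benefits of amisulpride will be most apparent on hostility, suspiciousness, hallucinations, tension, uncooperativeness and motor hyperactivity sub-scores of the BPRS". This is a comparison within the scale: the effect on these items is expected to exceed the effect on the rest.

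Section 3 (Outcome measures) defines the full scale: "The total score is obtained by summing the scores from the 18 items".

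Section 5.1 builds one six-item sum. It introduces the items thus: "In particular the Hostility, Suspiciousness, Hallucinations, Unusual Thought Content, Tension, and Uncooperativeness items of the BPRS all assess important areas of psychopathology". It gives the range: "Scores on the subset range from 6 to 42, with higher scores indicating greater levels of psychopathology". The analysis is a single sentence: "The sub-score will be analysed in the same way the full BPRS analysis, for both Stage 1 and Stage 2". For Stage 1 that means the repeated measures model comparing arms A and B combined with arm C. For Stage 2 it means the analysis of covariance comparing A with B. Each estimates a treatment difference and tests it against zero.

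The SAP plans no score for the other 12 items, no contrast between the two sets, and no rule for judging where benefit is greatest. The interaction tests in section 5.4 concern patient subgroups, not BPRS items.

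**The concern.** The hypothesis and the test ask different questions. The hypothesis asks whether the effect on six items exceeds the effect on the other twelve. The test asks whether the effect on six items differs from zero. Because the six items are nested in the total, a drug that lowered every BPRS item equally would lower the sub-score as well, and the planned test could be significant although the hypothesis was false.

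At stake is the interpretation of a pre-specified hypothesis that sits within a primary objective. With no comparative analysis planned, the sub-score result is the most direct evidence the report will have on it, and that evidence cannot separate a general effect from a concentrated one.

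**Working it through.** **Inputs from the SAP.** Effect of interest: the minimal relevant difference "is considered to be 5 points on the BPRS" (section 3, Sample size considerations). From the same section: SD 9, 90 of 100 patients assessed, two-sided 5% level, stated power 70%. Items: 18 in total, 6 in the sub-score, so 12 outside it.

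**Assumptions.** Equal allocation to the three arms, so A+B v C is 60 v 30. The SAP gives no sub-score SD, so it is derived from the total SD of 9 with equal item variances and a common inter-item correlation ρ, varied from 0 to 0.5. The calculation is a two-group normal comparison at one time point, without covariate adjustment.

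**Step 1: the SAP's own figure.** SE = 9 × √(1/60 + 1/30) = 9 × 0.2236 = 2.01. 5/2.01 = 2.48, and 2.48 − 1.96 = 0.52, so power is 0.70. The stated 70% reproduces.

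**Step 2: an even effect, so the hypothesis is false.** Effect per item = 5/18 = 0.28. Effect on the sub-score = 5 × 6/18 = 1.67 points. Per-item difference between the six and the twelve = 0.

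**Step 3: SDs.** Item variance s² = 81 / [18(1 + 17ρ)]. Sub-score SD = √[6s²(1 + 5ρ)]. SD of the contrast (mean of six minus mean of twelve) = √[s²(1 − ρ)(1/6 + 1/12)].

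Example at ρ = 0: s² = 4.5 and sub-score SD = √27 = 5.20. SE = 5.20 × 0.2236 = 1.16. 1.67/1.16 = 1.43, and 1.43 − 1.96 = −0.53, so the probability is 0.30.

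**Step 4: chance of a significant planned sub-score test under the even effect.**

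| ρ | Sub-score SD | P(significant) | Correlation of sub-score with total |
|---|---|---|---|
| 0 | 5.20 | 0.30 | 0.58 |
| 0.1 | 3.87 | 0.49 | 0.77 |
| 0.2 | 3.50 | 0.57 | 0.86 |
| 0.3 | 3.33 | 0.61 | 0.90 |
| 0.5 | 3.15 | 0.66 | 0.95 |

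In the same case a six-versus-twelve contrast has a true value of zero, so it is significant in 5% of trials.

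**Step 5: could the contrast detect concentration?** If two thirds of the 5 points fell on the six items, the per-item difference would be 3.33/6 − 1.67/12 = 0.556 − 0.139 = 0.417. Power would be 0.42 at ρ = 0, 0.86 at ρ = 0.1 and 0.98 at ρ = 0.2. If only half fell there, the difference would be 2.5/6 − 2.5/12 = 0.208 and power 0.14, 0.33 and 0.54 at the same correlations.

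**Step 6: the item lists.** Objective 1 names motor hyperactivity and not Unusual Thought Content. Section 5.1 has Unusual Thought Content and not motor hyperactivity. Five of the six items match.

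**The case against.** The strongest reply is that nothing the SAP states here is shown to be false. A reader might infer that the authors intend to report a significant sub-score as confirming the hypothesis. The SAP does not say so. Section 5.1 justifies the sub-score by the items' clinical importance and by their being the domains the disorder most affects, which is a different matter from where treatment works best. For a targeted symptom outcome, a test against zero is ordinary practice. This stands, and the point is limited to the absence of a comparative test.

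It may also be tempting to read 0.30 to 0.66 as a false-positive rate. It is not: the sub-score effect of 1.67 points is real in that scenario, so these are power figures. Setting them beside 5% compares tests of two different hypotheses.

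Nor is the plan silent on the question. The sub-score and total are estimated in the same patients with confidence intervals, so a total effect without a sub-score effect would count against the hypothesis. A rough effect on the other twelve items follows by subtraction. What that does not give is an interval for the difference between the sets.

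Finally, the contrast is imperfect. Items are scored from 1 (not present), and the lowest baseline band in section 5.4 starts at 30. At that total the average item is only (30 − 18)/18 = 0.67 points above its floor. Items absent at baseline cannot improve, so a proportional, non-selective effect could produce a non-zero raw contrast if the six items are the more severe ones. The 5% rate holds only for an exactly even additive effect. The hypothesis could also be meant on a standardised scale rather than per item. These are reasons to define the contrast carefully and interpret it with care; they do not make the sub-score test comparative.

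**Conclusion.** The point holds as a mismatch between a stated comparative hypothesis and a non-comparative analysis. A significant sub-score would show an effect on those items, not that the effect is concentrated there. Under an even 5-point effect the planned test would be significant about 30% to 66% of the time while giving no support for selectivity. That range rests on 60 v 30 patients, total SD 9, equal item variances and inter-item correlations of 0 to 0.5; only the total SD and the 90 assessed patients come from the SAP.

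A reader might conclude that the primary analysis is compromised. It is not: the total-BPRS comparison and its 70% power are unaffected. The issue is the interpretation of a subsidiary hypothesis, and the change is worth making because it is cheap.

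**What to change.** 1. Reconcile the item lists in objective 1 and section 5.1, so that the hypothesis and the sub-score name the same six items.
2. Keep the sub-score analysis as planned.
3. For Stage 1 at week 12, add the same model for the sum of the remaining 12 items, and one contrast: each patient's mean over the six items minus the mean over the other 12, adjusted for its own baseline value, reported with a 95% CI.
4. State that the sub-score result alone will not be taken as support for greater benefit on the six items.
5. State that the contrast is on the raw per-item scale and will be interpreted with regard to floor effects on items absent at baseline.

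The cost is some SAP wording, a parallel run of the existing model on the 12 items, and one extra contrast model, all on data already collected. The downsides are that a claim of concentrated benefit becomes harder to make, and that the contrast may have limited power if the items are only weakly correlated.

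### Section 5.2 reads a flat Simpson-Angus course as no drug effect, but after weeks 10-12 that course rests on changing sets of patients and on no stated comparison between arms

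*SAP*

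**What the plan says.** Section 5.2 gives the Simpson-Angus Scale (SAS) method in two steps. First: "The change in SAS scores will be plotted over time to see if there appears to be any increases over time". Then the reading of the plot: "If the SAS scores remain constant over the assessment time points we can assume that amisulpride is having no effect on Extrapyramidal side effects". It names no arm, test or interval, and does not mention schedule version.

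Section 3 (Secondary Efficacy Parameters, item i) lists the SAS visits as baseline, week 4, weeks 10-12, week 16 and a final visit at weeks 22-24, which was at first weeks 34-36. It also promises a comparison that 5.2 does not repeat. SAS change from baseline to week 10-12, and change "between week 10-12 and the final assessment (week 22-24 or 34-36) will be compared between groups to assess EPSE".

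The schedule changed during the trial. Section 3 (Primary objectives, item 2): "Duration of stage 2 treatment was initially 24 weeks but was then reduced to 12 weeks". Section 5.1: "the protocol has now been amended to shorten Stage 2 to 12 weeks with an additional assessment at about week 16". The same paragraph of 5.1 says of Stage 2: "Most patients will have only one outcome time point at week 24 or 36". The randomisation table in section 3 shows arm B moving from amisulpride to placebo and arm C from placebo to amisulpride after week 12.

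**The concern.** Section 5.2 turns the shape of a time course into a conclusion about harm. That needs successive points on the plot to describe the same patients after comparable exposure. In Stage 2 they need not. Patients followed under the initial schedule have no week 16 visit, and the final visit comes after a Stage 2 of 12 or 24 weeks.

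If patients on the two schedules differ in mean SAS change, the plotted line moves between weeks 10-12 and later visits for that reason alone. A real rise could look flat and be reported as no extrapyramidal effect, or a flat course could look like a rise. For the BPRS, section 5.1 recognises the irregular Stage 2 visits and responds with an analysis of covariance on the week 12 score. Section 5.2 makes no such provision for the SAS.

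**Working it through.** **The plan's own figure.** The SAP gives no SAS mean, standard deviation or power. Its one power figure is for the BPRS. With 60 versus 30 patients (2:1, assuming equal arms), 5 / (9 × √(1/60 + 1/30)) = 2.48, and 2.48 − 1.96 = 0.52, which gives 70% power as stated. The point here does not depend on it.

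**Who supplies each visit** (sections 3 and 5.1):

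| Visit | Scheduled for |
|---|---|
| Baseline, week 4, weeks 10-12 | all patients |
| Week 16 | amended schedule only |
| Weeks 22-24 | amended schedule |
| Weeks 34-36 | initial schedule |

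The Stage 1 visits lose patients only by dropout. On a literal reading, the statement in 5.1 that most patients have a single Stage 2 time point puts week 16 coverage below half. It does not bound coverage at weeks 22-24.

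**A shift with no true change.** Let f be the share of patients on the initial schedule, a their mean change from baseline, and b the mean change of those on the amended schedule. Suppose every patient is flat after week 4.

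- Mean at weeks 10-12: f·a + (1 − f)·b
- Mean at week 16: b
- Apparent shift: b − [f·a + (1 − f)·b] = f·(b − a)

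The SAP gives none of f, a or b. Taking a = 1 and b = 2 as assumptions:

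| f | Weeks 10-12 | Week 16 | Apparent shift |
|---|---|---|---|
| 0.50 | 1.50 | 2.00 | +0.50 |
| 0.65 | 1.35 | 2.00 | +0.65 |
| 0.80 | 1.20 | 2.00 | +0.80 |

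With a = b, every shift is 0.

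**The final visit.** The result depends on how it is plotted, which the SAP does not say.

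- As two separate points: 2 at weeks 22-24 and 1 at weeks 34-36, an apparent drop of 1.0 with no patient changing.
- As one pooled final assessment: f·1 + (1 − f)·2, equal to the weeks 10-12 value, so no shift. The pooled point then mixes two lengths of Stage 2. With an assumed true slope of 0.05 points per week after week 12, the change is 12 × 0.05 = 0.6 on the amended schedule and 24 × 0.05 = 1.2 on the initial one. The pooled value is 1.2f + 0.6(1 − f), or 0.90, 0.99 and 1.08 for f = 0.50, 0.65 and 0.80.

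**A real rise that looks flat.** Suppose each patient rises by 1 point after weeks 10-12, and the amended-schedule patients' mean change is lower by d. The plotted movement at week 16 is 1 − f·d. It is zero when d = 1/f, that is 2.0, 1.54 and 1.25 points for the same three values of f.

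**What removes the offset.** If Stage 2 change is taken within patient from weeks 10-12, the flat example gives b − b = 0. A contrast of randomised arms at the same visit compares patients on the same schedule and is not biased by the change in schedule either.

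**The case against.** The strongest reply is that section 3 already promises the right analysis: SAS change over each stage, compared between groups, with the two final visits treated as one assessment. On that reading, within-patient Stage 2 change removes any constant difference between the two sets of patients, no step from week 24 to week 36 exists, and only week 16 rests on a subset. The quantity plotted is change, so differences in baseline SAS level drop out. Stage 1, the placebo-controlled period, is untouched. Nothing in the SAP suggests that earlier and later patients differ in SAS change.

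Most of this stands and limits the point. A reader might infer that the time plot is the only SAS analysis in the plan, or that the whole plot joins different patients. Section 3 and the Stage 1 schedule contradict both.

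It does not rescue 5.2. The proposed-analyses section does not carry the comparison through and states a different decision rule. Plotting change removes differences in level but not in mean change from baseline. Pooling the final visits replaces one problem with another, because the point then mixes 12 and 24 weeks of Stage 2.

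**Conclusion.** The point holds for Stage 2. After weeks 10-12, the course of SAS change can move with who was measured or with the length of Stage 2, so a flat line cannot be read as absence of a drug effect. The schedule change does not affect Stage 1.

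No size can be derived from the documents. The shift of 0.50 to 0.80 points rests on an assumed 1-point difference in mean change and on f between 0.50 and 0.80; equal mean change gives zero. It would go too far to say that a bias is present, that weeks 24 and 36 will be drawn as separate points, or that fewer than half of patients have the weeks 22-24 visit. The SAP supports none of these.

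The schedule problem is secondary to the missing comparator. Arms B and C switch treatment after week 12, so a pooled Stage 2 course could not isolate the drug even on one uniform schedule. Both problems are in the same two sentences of 5.2 and should be corrected together.

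**What to change.** In section 5.2:

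- Delete the rule that constant SAS scores mean no effect.
- Estimate within-patient SAS change by randomised arm with 95% confidence intervals: baseline to week 10-12 for arms A and B together versus C, and week 10-12 to the final assessment for A versus B.
- Adjust each comparison for the starting SAS value and, in Stage 2, for schedule version.
- Keep the plot as description only, by arm, with the number measured at each visit and the week 24 and week 36 final visits marked as belonging to different schedules. Draw no time trend between visits supplied by different patients.

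This brings 5.2 into line with section 3. It needs SAP wording and a little programming, and no new data. Stage 2 intervals will be wider, since only arms A and B contribute.

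Separate panels by schedule version, or a model with visit, arm and schedule interactions, are optional. With 100 patients, three equal arms and 40% on the amended schedule (the last two assumed), each arm on that schedule holds 100/3 × 0.4, or about 13 patients, before dropout.
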